## **PURPOSE OF STUDY**

The purpose of this clinical study is to determine the effectiveness of the Erchonia® EVRL (manufactured by Erchonia Corporation (the Company)), when both the red and violet diodes are activated simultaneously, in providing temporary relief of minor chronic neck and shoulder pain of musculoskeletal origin.

## **STUDY DURATION**

The estimated total duration of the study is two days (48 hours).

## **INDICATION FOR USE**

The indication (claim) being sought through support of the results of this clinical study is: "The Erchonia® EVRL is indicated for adjunctive use in providing temporary relief of minor chronic neck and shoulder pain of musculoskeletal origin"

It is intended that the results of this clinical study be used to support a 510(k) submission to FDA for clearance to market the device for the intended indication.

## **EXPECTED RESULTS**

Following completion of the study treatment administration protocol with the Erchonia® EVRL, it is anticipated that compared with when treatment administration occurs with the Erchonia® EVRL red diode only activated, application of treatment administration with the Erchonia® EVRL with both the red and violet diodes activated simultaneously will yield comparable (equivalent) or better (superior) results with respect to decrease in subjects' neck and shoulder pain on the 0-100 VAS relative to baseline.

## **REGULATORY BACKGROUND**

This clinical study protocol is based on the clinical study whose results supported the following FDA market clearances for the indication of "adjunctive use in providing temporary relief of minor chronic neck and shoulder pain of musculoskeletal origin."

- K050672: Erchonia® EVRL Laser (in red diode mode)
- K101430: MLS-AC Derma Scanner™ (in red diode mode)
- K100509 & K130741: Erchonia® THL1 Laser & Erchonia® PL5000
- K130996: Erchonia® XLR8™:

## **DEVICE INFORMATION: ERCHONIA® EVRL**

### **REGULATORY BACKGROUND**

The Erchonia® EVRL Laser being evaluated in this clinical study for adjunctive use in providing temporary relief of minor chronic neck and shoulder pain of musculoskeletal origin has received FDA clearance under **K050672** for the following indication:

The Erchonia EVRL Laser is generally indicated:

- a. while using the red diode, for adjunctive use in providing temporary relief of minor chronic neck and shoulder pain of musculoskeletal origin, and
- b. while using the blue diode, to treat dermatological conditions, and specifically indicated to treat moderate inflammatory Acne Vulgaris.

However, its application in this clinical trial is experimental, as it is the goal of the current study to demonstrate non-inferiority in efficacy of the Erchonia® EVRL when used in simultaneous dual diode mode (both the red (640 nm) and violet (405 nm) diodes activated simultaneously) compared to its use with the red diode only activated.

### **DEVICE DESCRIPTION & DETAILS**

The Erchonia® EVRL (Model# EVRL) used in this study is a hand held low level laser that uses two semi-conductor diodes; a 640 nanometer (visible red light) and a 405 nanometer (visible violet light), each emitting its wavelength with a tolerance of  $\pm 10$  nanometer. The lasers are powered by an internal battery that is recharged using a separate inductive charging base powered by an external class II medical power supply. This configuration offers portability as well as consistency of power. The Erchonia® EVRL is a variable hertz device. The variable hertz feature of the Erchonia® EVRL is a pulsed wave, defined as containing a selected series of breaks, variances that are preprogrammed.

The internal battery powers the two specially created and patented electronic diodes with an output of 7.5mW red  $\pm$  1 mW and <5mW violet laser.

The device contains software that is embedded in a RAM chip on the PCB. This data includes the touch screen images (GUI) and the command prompts that activate the screen icons; work in conjunction with the component platform to ensure the device operates as intended. The exterior materials consist of 6061 T6 AL and Copolymer Acetal with powder coating finish.

The Erchonia® EVRL has the following specifications:

#### **Device**

- Weight: Laser-.95lbs / .42kgs. Charger Base-.55lbs / .42kgs
- Full Color TFT Touch Screen Module
- Machined billet aluminum enclosure
- Dimensions: Laser-Length-6.9" (17.52cm) Width-3.10" (7.87cm) Depth-.76" (1.93cm), Charger Base- Length-5.7" (14.47cm) Width-3.5" (8.88cm) Depth-1.65" (4.19cm)

### **Laser**

- 2 electronic diodes, with patented optics
- Output: 640 nm 7.5mW  $\pm$  1mW (red)
- Output: 405 nm <5mW (violet)
- Wavelengths: 640 nm & 405nm +/- 10nm
- Duty Cycle: 50%

### **Power**

- Battery: Lithium-ion Polymer 3.7V, 1500mAh, 5.6w

### **Inductive Charging Base**

- 1.5A 12V

### **External Power Supply**

- Model: ER-E-00182
- 100-240Vac, 50-60Hz, 0.5A; 12Vdc 1.5A

### **Dosage calculations for the Erchonia® EVRL**

Total energy per diode:

- (diode output means) mW / 1000 (converting mW to W) \* (time in seconds)  $\div$  2 (50% duty cycle) = (total energy per diode per minute)
- 640 nm diode (red):  $7.5 / 1000 * 60 \div 2 = .225J$
- 405 nm diode (violet):  $4.5 / 1000 * 60 \div 2 = .135J$
- Total device diodes energy per minute: .36J
- The Erchonia® EVRL used in this study is shown in Figure 1 below.

Figure 1

The following diagram identifies each component of the device and a complete description of the component follows.

Figure 2

#### **#1 POWER BUTTON (ON/OFF)**

The Power Button allows you to turn the device ON “I” or OFF “O”. To turn the device ON, press and Hold this button, after approximately 3 seconds the green (#2 Power On Light) turns on. To turn off the device it is recommended to use the “**Powering Down**” method, explained in the **Operation Section** of the manual. In the unlikely event that your device stops responding to touches, by pressing and holding the power button for 15 seconds will force shut down the device. This is only recommended if the device cannot be turned off from the “**Powering Down**” method.

#### **#2 LASERS ON LIGHT**

The “Lasers On” light is an LED indicator that will light up when the Lasers are ON and turn off when the lasers are OFF.

#### **#3 POWER ON LIGHT**

The “Power On” light is an LED indicator that will display a constant green light when the device is powered on and turn off only when the device is OFF.

#### **#4 TOUCH SCREEN**

The touch screen functions as a display screen and an input panel, providing information and a means to operate the device by touching the appropriate icon.

### **#5 PIVOTING LASER MOUNT**

The Pivoting Laser Mount allows you to adjust the laser angle (up to 20° each direction) based on your preference.

### **#6 LASER DIODES**

The Lasers consist of two electronic laser diodes, with patented optics. These laser diodes when activated by the internal power source generate laser energy thereby emitting on one side a red beam and the other side a violet beam. This is a specially designed and patented device created to ensure the laser beam is focused and directed for the most optimal use. The device can be programmed with up to 4 defined Hz frequencies (two for each diode).

#### **CHARGER BASE**

Directions to set Device on Charger Base

[figure not shown]

Figure 3

#### **POWER SUPPLY**

Figure 4

**#1 INDUCTIVE CHARGER BASE**

The Inductive Charger Base is a custom based system specifically designed to charge the laser device. It is an inductive charging system that charges the device wirelessly. The Charger Base must be plugged into the power supply and the power supply must be plugged into a wall socket for Charger Base to receive power. Once powered up, the Laser device is placed on Charger Base with the touch screen facing up and Laser diodes facing away from Charger Base LED lights.

**#2 CHARGER BASE POWER LIGHT**

The Charger Base “Power” Light is the power indicator LED that will light up when the energized Power Supply connector is plugged into the Inductive Charger Base.

**#3 DOCKED LIGHT**

The “Docked” light is an indicator LED that will light up to indicate the device is correctly docked in the inductive charger base. The LED will flash ON and OFF when correctly in place and turn off when removed from the inductive charger base.

**#4 CHARGER BASE CONNECTOR PORT**

The Charger Base Connector Port is the location to plug the Power Supply Connector in to supply power to the inductive charger base.

**#5 POWER SUPPLY CONNECTOR**

The Power Supply Connector plugs into the Inductive Charger Base Connector Port to provide power to charger base.

## DEVICE SAFETY

### RISK AND PREVENTION OF EYE INJURY

The Erchonia® EVRL is classified by the FDA/IEC as a Class 2 laser device. This designation represents a current standard for use in order to ensure the safety of the subject. A Class 2 laser is determined to have a chronic viewing hazard. Pointing the laser beam directly into the eye and maintaining it there for an extended period of time could prove to be damaging.

To ensure there is no possible instance of residual effect, eye protection is implemented for the subject receiving the laser procedure administrations.

A pair of safety glasses is provided for use during all procedure applications. These safety glasses are Kentek PN: C22-KMT-6101. The safety glasses, sufficiently and effectively block the laser light spectrum at OD 2+ @ 635nm, OD 0.75 @ 405nm VLT 60%.

- Height: 40 mm
- Width: 145 mm
- Length: 165 mm

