### OTHER POTENTIAL RISKS

Other potential risks and their mitigation include:

- Electric shock: operator risk only: mitigated through electrical safety testing.
- Electromagnetic interference: mitigated through EMC/EMI testing.
- User error: mitigated through instructions for use documentation.

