## **PROCEDURE ADMINISTRATION PHASE**

### **PROCEDURE ADMINISTRATION PROTOCOL**

- The procedure administration phase of the study directly follows successful completion of the pre-procedure evaluations phase, on the same day.
- The procedure administration phase comprises a single procedure administration with the Erchonia® EVRL.
- The procedure administration lasts a total of 13 minutes.
- The procedure administration with the Erchonia® EVRL is administered at the test site.
- The procedure administration protocol is identical to that in the retrospective control study, and is as follows:
  1. The subject enters the procedure room and is seated comfortably.
  2. The subject is correctly fitted with the protective eyewear.
  3. The Erchonia® EVRL is positioned and centered 6 inches above the subject's sagittal suture (top of the head).
  4. One minute of pulsed laser is applied to the sagittal suture (top of the head).
  5. Two minutes of pulsed laser is then applied to the left cervical, shoulder and torso area. The laser is applied starting in the cerebral region, at the top of the ear, lasering left cervical anterior and posterior muscles, working the laser down into the left shoulder and torso anterior and posterior muscles.
  6. Step 5 is repeated to the subject's right cervical shoulder and torso area.
  7. One minute of pulsed laser is then applied to right shoulder during passive external rotation of the shoulder. The anterior muscles of the right shoulder (pectoralis group) are lasered, with the subject's arm bent at the elbow.
  8. One minute of pulsed laser is then applied to the right shoulder during passive adduction of the subject's right arm and shoulder. The posterior muscles of the right shoulder are lasered.
  9. One minute of pulsed laser is then applied to the right cervical muscle and trapezius muscle during passive left lateral flexion of the cervical spine. Starting in the neutral position of the head, the laser light is applied to the right cervical muscles and right trapezius muscles.
  10. One minute of pulsed laser is then applied to the right sternocleidomastoid and scalene muscles during passive range of motion. The laser light is applied to the right sternocleidomastoid and scalenus muscles.
  11. Step 7 is then repeated to the left shoulder.
  12. Step 8 is then repeated to the left shoulder.
  13. Step 9 is then repeated to the left cervical spine.

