## **ADVERSE EVENTS**

At each evaluation point throughout the clinical study, and at any other time throughout the duration of the clinical trial that is necessary, any and all potential adverse events reported by a subject or observed by an investigator will be recorded on the case report form, and subsequently evaluated by a suitably qualified independent reviewer for determination of relationship to the study treatment and whether or not any corrective action needs to be taken. All potential adverse events recorded will be appropriately reported to the governing IRB, as applicable.

It is unlikely and not expected that any adverse events will result from implementation of this clinical study protocol. Prior clinical trials using low level laser light have not typically yielded any adverse events or reactions. However, potential adverse events that may feasibly occur from application of the Erchonia® EVRL include, but are not necessarily limited to: skin irritation, discoloring, rash, indentations and infection.

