**Please mark any of the boxes below that are applicable:**  
The subject's reported adverse event can be categorized as follows:

	skin irritation
	itching
	discoloring
	rash/hives
	indentations
	pain/discomfort
	other: _____

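### Eye injury is the only subject hazard with its own risk section, but no listed event, named category or adverse event question mentions eyes or vision, so capture is less sensitive than it could be, chiefly at 24 and 48 hours

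*Combined protocol and SAP*

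**What the plan says.** Under Device Safety (repeated in Appendix A) the protocol has a section on the risk and prevention of eye injury. It states: "A Class 2 laser is determined to have a chronic viewing hazard", and continues: "Pointing the laser beam directly into the eye and maintaining it there for an extended period of time could prove to be damaging". The control is protective eyewear, fitted before the laser is applied and removed at the end. The remaining hazards share one short list under Other Potential Risks: electromagnetic interference, user error, and "Electric shock: operator risk only: mitigated through electrical safety testing".

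The Adverse Events section says that potential events "include, but are not necessarily limited to" the following: "skin irritation, discoloring, rash, indentations and infection". It also requires that every potential event reported by a subject or observed by an investigator be recorded, and that a qualified independent reviewer judge its relationship to treatment.

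In Appendix C, the Investigator's Adverse Events Record Sheet says that the subject's "reported adverse event can be categorized as follows". Six named boxes follow (skin irritation, itching, discoloring, rash/hives, indentations, pain/discomfort), then a free-text box for anything else. The endpoint form asks whether a potential event was observed by the investigator or reported by the subject. The 24-hour and 48-hour forms, completed at home, ask whether the subject thinks he or she is experiencing an event caused by the device treatment.

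**The concern.** A safety plan normally asks about the hazard that it has itself singled out. Here the hazard with its own section does not appear by name anywhere in the tools that collect adverse events. The procedure is carried out on the head and neck: one minute over the top of the head, and then "The laser is applied starting in the cerebral region, at the top of the ear", moving downwards. Simultaneous red and violet use is described as experimental, and the results are meant to support a 510(k) submission.

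The home forms are also narrower than the Adverse Events section. That section wants all potential events, with relationship judged afterwards by an independent reviewer. The home question makes the subject judge relationship first, and it is in the present tense. A subject whose blurred vision lasted an hour, or who did not connect it with a neck and shoulder treatment, could correctly tick No. At stake is how much weight a report of no eye events could bear.

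**Working it through.** **Step 1. Set the hazard beside each collection item.**

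| Place | Items | Naming eyes or vision | Depends on |
|---|---|---|---|
| Adverse Events, potential events | 5 | 0 | open-ended list |
| Record sheet, named boxes | 6 (plus free text) | 0 | an event having been raised |
| Endpoint question | 1 | 0 | subject report or investigator observation; no attribution |
| 24-hour home question | 1 | 0 | subject thinks a current event comes from the treatment |
| 48-hour home question | 1 | 0 | same as at 24 hours |

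The totals are 0 of 5 listed events, 0 of 6 named boxes and 0 of 3 questions. The outcome assessments listed for the endpoint, 24 hours and 48 hours contain no eye assessment either.

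**Step 2. See where sensitivity is lost.** The endpoint question is broad, but the evaluation takes place within 3 minutes of the end of the procedure. Later symptoms therefore depend mainly on the two home forms, where attribution and present tense both filter the answer.

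**Step 3. What zero events would show.** The plan states no figure for eye events, so there is nothing to reproduce. The planned enrolment is 43. With no events among *n* subjects, the exact one-sided 95% upper bound solves (1 − p)^n = 0.05:

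p = 1 − 0.05^(1/43) = 0.0673, or 6.7%.

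This assumes that all 43 answer and that every occurrence of what is being counted is captured. With a direct question, what is counted is self-reported eye symptoms. With the general questions alone, the same figure bounds only events that were reported or observed in answer to those questions.

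**Step 4. What reduced capture could mean.** The documents give neither a true rate nor a capture fraction, so both are assumptions here. The chance of recording at least one event is 1 − (1 − p·c)^43, where p is the true rate and c the fraction captured.

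| Assumed true rate | c = 1 | c = 0.5 |
|---|---|---|
| 1% | 35% | 19% |
| 2% | 58% | 35% |
| 5% | 89% | 66% |

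For example, at 2% with half captured, 1 − 0.99^43 = 35%. The table shows only the direction and possible size of the loss; the value c = 0.5 is not an estimate.

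**The case against.** The strongest reply is that nothing blocks the recording of an eye event. The list of potential events is open-ended. All reported or observed events must be recorded, at each evaluation point and at any other time needed. The endpoint question requires no attribution and includes what the investigator sees. The pain/discomfort box is not limited by body site and could hold eye discomfort, and a vision change fits the free-text box. The record sheet then asks for a description, severity, causality and action taken. All of this stands. A reader might infer from the counts above that eye events surface only if the subject volunteers them and blames the laser, or that nobody asks, or that zero events would support no bound at all. The documents do not support those readings: subjects or investigators face a general question at three time points, and attribution is required only at two.

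It can also be said that the stated hazard is conditional on a sustained beam into the eye, that no step aims at the face, and that eyewear is worn throughout. That is fair, and it lowers the expected rate. It does not explain why the named hazard is left out of the forms. A reader may notice that the eyewear is rated OD 2+ at 635 nm but OD 0.75 at 405 nm; this point draws no conclusion about whether the eyewear is adequate.

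The event list and the record sheet also differ on infection, itching and pain/discomfort. As both are open-ended, that is editorial and not part of this point. The consent form was not available, so whether it tells subjects about eye symptoms cannot be judged.

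**Conclusion.** The point holds as one of reduced sensitivity. The plan names eye injury as a hazard in a section of its own, yet 0 of 5 listed events, 0 of 6 named boxes and 0 of 3 questions mention eyes or vision. The loss falls mainly at 24 and 48 hours, where the home forms collect less than the Adverse Events section asks for. How many events would be missed cannot be derived from the documents.

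With a direct question, 0 of 43 would support an upper bound of 6.7% for self-reported eye symptoms, provided all 43 answer. It would not bound eye injury, because no eye examination is planned and none is proposed here. The primary efficacy analysis is unaffected. This is a cheap and worthwhile improvement to safety data collection; it does not show that eye events would go unrecorded.

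**What to change.** 1. Add one yes/no line to the endpoint, 24-hour and 48-hour forms, for example: *Any new eye discomfort or change in vision since the treatment?* It should not ask the subject about cause; the independent reviewer does that.
2. Add an eye or vision symptom to the potential events under Adverse Events and to the boxes on the record sheet.
3. Under Safety Analyses, report this count separately, with its denominator. Keep these solicited reports out of the between-group chi-square test, or mark them there. The documents show no matching eye question in the reference study, so a difference could reflect the asking alone.

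The cost is one line on three existing forms, one list entry, one box and one table row, with no extra visit, examination or staff and no change to treatment. The downside is that a direct question may draw a few trivial reports.

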### FOOD AND DRUG ADMINISTRATION (FDA) DETERMINATION OF NON-SIGNIFICANT RISK (NSR) STATUS

The Food and Drug Administration (FDA) has determined the Erchonia® EVRL to be non-significant risk (NSR) through the following 510(k) clearance:

**K050672: Erchonia® EVRL Laser:** The Erchonia EVRL Laser is generally indicated:

- while using the red diode, for adjunctive use in providing temporary relief of minor chronic neck and shoulder pain of musculoskeletal origin, and
- while using the blue diode, to treat dermatological conditions, and specifically indicated to treat moderate inflammatory Acne Vulgaris.

### OTHER POTENTIAL RISKS

Other potential risks and their mitigation include:

- Electric shock: operator risk only: mitigated through electrical safety testing.
- Electromagnetic interference: mitigated through EMC/EMI testing.
- User error: mitigated through instructions for use documentation.

### LABELING

The Erchonia® EVRL to be used in this clinical study will be labeled, “CAUTION – Investigational device. Limited by United States law to investigational use.” Once the device has been cleared for market in the U.S., the device will be labeled as a prescription device, per 21 CFR § 801.109.

## **STUDY INDICATION, THEORY OF MECHANISM OF OPERATION, & SUPPORTING MATERIALS**

### **STUDY INDICATION: CHRONIC NECK AND SHOULDER PAIN OF MUSCULOSKELETAL ORIGIN**

#### Definition

Chronic pain of musculoskeletal origin arises from impairment of the muscles, ligaments and tendons, and bones. The neck refers to the cervical spine comprised of the top 7 vertebrae, the vertebral joints which connect them and the ligaments and muscles that provide neck stability, function, and movement. Impairment therein primarily results in pain and reduced range of motion in the neck and shoulders region.

#### Statistics

- Pain affects more Americans than diabetes, heart disease and cancer combined.
- In 2011, at least 100 million adult Americans reported chronic pain conditions, with women more likely to experience chronic pain than men.
- The total annual health care costs (medical costs and economic costs related to disability days and lost wages and productivity) related to treatment of chronic pain conditions in the United States ranges from \$560 billion to \$635 billion (averaging to about \$2,000 per U.S. adult).
- Chronic pain is reported to have a significant impact on quality of life: 59% report an impact on overall enjoyment of life; 77% report feeling depressed; 70% report trouble concentrating; 74% reported reduced energy level; and 86% report sleep disruption.
- The National Institute of Health Statistics survey reports chronic neck pain as being the second most common pain complaint (second to low back pain), experienced by 15% of the U.S. adult population at any one time.
- Over half (53%) of the workforce reports some form of musculoskeletal pain at any one time, and about 13% lost productive work time averaging 5.5 hours per week while experiencing musculoskeletal pain.

*Source: American Academy of Pain Medicine*

